#### 3.5 Secondary outcome measures

The secondary objective will be measured using the Client Service Receipt Inventory (CSRI), adapted for use for anxiety disorders in primary care and community settings, which is a measure of the full health and social care cost and patient cost of treatment. Additionally, the objective will be measured using the EQ-5D-5L, which is a participant-reported measure of health utility and quality of life used by NICE to generate QALYs for cost effectiveness assessments, and uses 6 items. Finally, the objective will be measured using the Work and Social Adjustment Scale (WASA) which is a participant-reported measure of work and social function, and uses 8 items.

- The outcome measure for **CSRQ** is the change in cost impact for previous 12 weeks from baseline to week 24.
- The outcome measure for **EQ-5D-5L** is the change for participants from baseline to week 24.
- The outcome measure for **WASA** is the change for participants from baseline to week 24.

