	
Alpha-Stim AID Cranial Electrotherapy Stimulations (CES) for participants with a primary working diagnosis of generalised anxiety disorder (GAD), in terms of health and social care service cost, and patient cost, from baseline to week 24, following previous treatment with low intensity psychological therapy intervention.
	
See Appendix B
 
The CSRI, adapted for use for anxiety disorders in primary care and community settings, is a measure of the full health and social care cost and patient cost of treatment.
 
The endpoint will be the cost impact from baseline to week 24.
 
EQ-5D-5L
 
See Appendix C
 
The EQ-5D-5L is a participant-reported measure of health utility and quality of life used by NICE to generate QALYs for cost effectiveness assessments. The EQ-5D-5L uses 6 items.
 
The endpoint will be the change in EQ-5D-5L for participants from baseline to week 24.
 
Work and Social Adjustment Scale (WASA)
 
See Appendix D
 
The WASA scale is a participant-reported measure of work and social function. The WASA scale uses 5 items.
 
The endpoint will be the change in WASA scale score for participants from baseline to week 24.

Tertiary
	
The tertiary objective of this study is to evaluate the clinical effectiveness of treatment with Alpha-Stim AID Cranial Electrotherapy Stimulations (CES) for depression and insomnia in participants with a
	
PHQ-9
 
See Appendix E
 
The PHQ-9 is a participant-reported measure of depressive symptomatology.

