**FUNDING AND SUPPORT IN KIND**

FUNDER	FINANCIAL AND NON FINANCIAL SUPPORT GIVEN
The Microcurrent Site Limited	
60 Alpha-Stim AID CES devices loaned to Nottinghamshire Healthcare NHS Foundation Trust for duration of study. Should all 60 devices be in use by participants concurrently, additional devices may be loaned to the Trust.
 
Consumables will be provided to the Trust, including AAA batteries, pregnancy testing kits, cleaning materials, conduction fluid and electrode pads.
 
Total funding of approximately £38,000.00 to Nottinghamshire Healthcare NHS Foundation Trust for study delivery costs.

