## **8.2 End of study provision**

The device is marketed and sold in the UK by the sponsor legal representative, and are available from private purchase at a cost of £499.00. Participants will be fully informed that participation in the study will result in a maximum of 12 weeks of Alpha-Stim AID device treatment, after which time point the device must be returned to the research nurse. Participants will not be encouraged to purchase a device, but will be advised by the research nurse if an interest is expressed. Participants will not receive a discount on the purchase of a device.

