## **11 STATISTICS AND DATA ANALYSIS**

### **11.1 Sample size calculation**

If Alpha-Stim AID CES has a comparable effect to IAPT high intensity psychological therapy interventions in patients with a primary working diagnosis of GAD, it will achieve an effect size of 1.04 (95% CI 0.88 to 1.23) in an intention to treat sample of 4,183 participants with pre-treatment GAD-7 score of 14.06 (s.d. 5.11) and post treatment GAD-7 score of 8.10 (s.d. 6.37) (Richards and Borglin, 2011). Reliable improvement was obtained after IAPT treatment for generalised anxiety disorder in 54.7%, reliable improvement plus clinically significant change in 40.1% and recovery in 46.0%.

However, to make a meaningful economic impact on NHS care, then Alpha-Stim AID CES does not need to be as effective as IAPT high intensity psychological therapy interventions. In a previous randomised controlled trial (Barclay and Barclay 2014), Alpha Stim CES reduced the mean Hamilton Anxiety score from 29.5 to 13.4 while sham Alpha Stim CES reduced it from 27.6 to 20.0 over 5 weeks  $p=0.001$ ,  $d=0.94$ , with 83% patients showing a drop of 50% in HAM-A score.

A meta-analysis of 14 Alpha Stim CES randomised controlled trials estimates an average effect size of 0.60. On this basis reliable improvement may be seen in 33%, reliable improvement plus clinically significant change in 24% and recovery in 28% cases.

The cost of IAPT high intensity psychological therapy intervention is estimated to be £2,895.00 per participant and £2,914.00 if stepped care was involved (Radhakrishnan et al, 2013). On a cost offset basis if Alpha-Stim AID CES cost £465.00, then reliable improvement plus clinically significant change (which would not necessitate high intensity treatment) in only 20% would be clinically and cost effective.

Taking all data into account, 60 patients would be required to complete Alpha Stim AID CES treatment and all assessments. However, to allow for drop-out from assessments, drop-out from Alpha-Stim AID CES, and choice in relation to IAPT high intensity psychological therapy intervention ,120 patients will be recruited.

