#### Any primary and community care contacts over the last 3 months

Indicate yes or no, by marking with a cross (X) in the relevant box.

	Yes	No
Participant has used any primary and community care services in the last 3 months		

If yes, provide further detail below.

	Service	Total number of contacts in last 3 months	Average duration of each attendance (minutes)
1	GP surgery		
2	GP home visit		
3	Practice nurse		
4	Community psychiatric nurse		
5	Walk-in centre		
6	Out-of-hours care		
7	Occupational therapist		
8	Social worker		

9	Advocate (eg, creative support)		
10	Home-help / home care worker		
11	Community support worker		
12	Psychiatrist		
13	Psychologist		
14	Other, please specify:		

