### Other costs

Indicate yes or no, by marking with a cross (X) in the relevant box.

	Yes	No
Participant has purchased any over-the-counter medicines or attended any private therapy sessions as a result of symptoms during the last 3 months (including herbal or complementary remedies (eg, crystals and visits to alternative practitioners)		

If yes, provide further detail below.

Medicine / preparation / herbal remedy bought or appointment with private practitioner	Total number of purchases or visits in last 3 months	Cost of each remedy or private session
1		
2		
3		
4		
5		
6		
7		

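### The only cost outcome, the CSRI, does not capture the device, its consumables or device training, and the plan does not say that any intervention cost will be added

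*Combined protocol and SAP*

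**What the plan says.** - **Cost measure.** Section 3.5 measures cost with the CSRI, "which is a measure of the full health and social care cost and patient cost of treatment". The EQ-5D-5L and WASA sit beside it but measure utility and function.
- **Cost outcome.** In section 3.5 it "is the change in cost impact for previous 12 weeks from baseline to week 24". The Study Summary words it differently: "The endpoint will be the cost impact from baseline to week 24". Neither mentions an intervention cost.
- **Questionnaire.** Appendix B covers income and benefits, time off work, hospital services, "Any primary and community care contacts over the last 3 months", travel, purchases, additional care and informal care. The item nearest to a device cost asks whether the "Participant has purchased any over-the-counter medicines or attended any private therapy sessions as a result of symptoms during the last 3 months".
- **Supply.** The funding table lists "60 Alpha-Stim AID CES devices loaned to Nottinghamshire Healthcare NHS Foundation Trust for duration of study", with consumables also provided to the Trust. Under section 7.4 the research nurse trains participants to use the device.
- **Prices.** Section 11.1 reasons "On a cost offset basis if Alpha-Stim AID CES cost £465.00". Section 8.2 says the devices are "available from private purchase at a cost of £499.00".
- **Analysis.** Section 11.3 promises means and standard deviations by visit. It has no unit costs and no costing method.

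**The concern.** Section 2 says the study is meant to supply evidence for NICE appraisal, including an assessment of economic impact. A cost outcome for that purpose has to contain the cost of the technology being appraised. Here the outcome is described as the full cost of treatment, yet it rests on a questionnaire that asks participants about services used and money spent. A device on free loan, free consumables and training by a study nurse leave no trace in it. The cost argument in section 11.1 does charge for Alpha-Stim, so the planning rationale and the outcome are not on the same footing. If the gap stays open, the price and the reuse assumption will be chosen after the results are known. The organisation that sells the device in the UK (section 8.2) is also the funder and is responsible for manuscript writing (Role Delegation).

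**Working it through.** **1. Where each intervention cost could be recorded**

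| Item | Supplied by | Entry in Appendix B | Linked to the cost outcome elsewhere |
|---|---|---|---|
| Device | Funder, on loan | None | No |
| Electrode pads, conduction fluid, batteries | Funder | None | No |
| Device training and support | Research nurse | None | No |

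Appendix B has free-text rows for other services, but no instruction to enter these items there.

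**2. Which weeks the outcome covers**

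- Baseline look-back of 12 weeks: about weeks −12 to 0.
- Week 24 look-back of 12 weeks: 24 − 12 = 12, so about weeks 12 to 24.
- Device treatment: weeks 0 to 6, or 0 to 12 at most (section 4).

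The two windows in section 3.5 do not overlap the treatment period, so a device entry in the questionnaire would still fall outside the outcome. A CSRI at week 12 would cover weeks 0 to 12. Sections 7.5 and 7.6 schedule one, but section 3.5 does not use it. The Study Flow Chart instead places the CSRI at week 6 and omits it at week 12. On that schedule the week 6 look-back ends at week 6 and the week 24 look-back starts at about week 12, so about weeks 6 to 12 would be covered by neither.

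**3. The plan's own cost figure**

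Section 11.1 takes £465 for Alpha-Stim, £2,895 for high intensity therapy (£2,914 with stepped care), and says that 20% not needing that therapy would be cost effective.

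- Offset at 20%: 0.20 × £2,895 = £579, and £579 − £465 = £114 net. With £2,914: £582.80 − £465 = £117.80.
- Break-even share: 465 / 2,895 = 16.1% (465 / 2,914 = 16.0%).

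The 20% is therefore sufficient but is not the break-even share, and its derivation is not given. The check shows only that the planning argument includes an intervention cost. These shares are not results of the outcome in section 3.5.

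**4. Size of the omission**

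Amount left out per participant = price / users per device. Total = 120 × that amount.

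| Price | Users per device | Per participant | 120 participants |
|---|---|---|---|
| £465 | 1 | £465.00 | £55,800 |
| £499 | 1 | £499.00 | £59,880 |
| £465 | 2 | £232.50 | £27,900 |
| £499 | 2 | £249.50 | £29,940 |
| £465 | 4 | £116.25 | £13,950 |
| £465 | 10 | £46.50 | £5,580 |

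Two users per device is 120 participants over the 60 loaned devices. Four and ten stand for reuse beyond the study. All the reuse rows are assumptions, because the documents give no device life or reuse rate. Consumables and nurse time have no unit cost in the documents, and section 11.1 does not say whether £465 includes them.

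**The case against.** A reader might infer that Alpha-Stim will be costed at zero. No text says so. Section 11.1 puts it at £465, and section 3.2 states the objective as service cost and patient cost without naming the CSRI, which is wide enough to admit an intervention cost. The supportable statement is that the stated outcome omits this cost and nothing says it will be added.

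A reader might also infer that any avoided service use would then appear as a net saving. The documents do not support that. The outcome is an uncontrolled change from baseline. Participants generally enter while waiting for high intensity therapy, so that course is not in their baseline look-back. Starting it would show as a rise, and avoiding it would not show as a fall. Appendix B also has no named row for IAPT or CBT sessions, only generic ones such as psychologist or other. Break-even shares with and without the device price therefore do not describe this outcome.

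It can further be said that the whole economic analysis is missing: service contacts have no unit prices either, and the device price is nearly a constant that can be added before analysis without new participant data. Both points stand, and they lower the severity. They do not remove the gap. For service contacts the quantities are at least collected within the outcome; for the intervention neither a quantity nor a price is tied to it. The price also depends on reuse and losses, which need a rule set in advance.

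**Conclusion.** The concern holds in this form: the only cost outcome does not capture the device, consumables or device training, its look-back in section 3.5 misses the treatment period, and the plan does not say that any intervention cost will be added. Followed as written, it understates the cost of the Alpha-Stim pathway by the whole intervention cost. That is £465 per participant if the planning value is charged to each, £499 at the private price, and less with reuse. These amounts rest on the assumption about users per device and on an undefined content for the £465.

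The two prices should not be read as a contradiction: one is a conditional planning value and the other a private purchase price. What is missing is a statement of which is the base case and what it includes.

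This should be fixed before analysis. It bears on the secondary objective and leaves the GAD-7 outcome and safety reporting untouched.

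**What to change.** - In section 3.5 and the Study Summary, define each participant's cost over weeks 0 to 24 as CSRI cost from the week 12 and week 24 administrations plus a prespecified intervention cost. Use the same wording in both places.
- Define the intervention cost as device, consumables issued, and nurse time for training and device support, kept separate from nurse time spent on research assessments.
- Reconcile the Study Flow Chart, which has the CSRI at week 6, with sections 7.5 and 7.6, which have it at week 12.
- Add a unit-cost table. State the base-case price of the intervention and what it includes before analysis.
- Prespecify sensitivity scenarios: one device per patient at £465 and at £499, and a reused loan device with a stated number of users and an allowance for devices lost or not returned.

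The cost is a short amendment, simple records of consumables, losses and nurse time, and a little more analysis. The cost result will be less favourable to the device.

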Treatment Procedure	
60-minute self-directed Alpha-Stim AID CES treatment sessions undertaken at participant's home, on a daily basis for 6 weeks for all participants. During this 6-week period, participants will be on the waiting list for high intensity psychological therapy intervention.
 
Following 6 weeks of Alpha-Stim AID CES treatment, participants have the option to receive a further 6 weeks of treatment, which is likely to coincide with start of high intensity psychological therapy intervention as clinically indicated.
 
Following a maximum of 12 weeks' treatment with Alpha-Stim AID CES, all participants will cease to receive treatment on study.
 
Participants will have 1x additional visit in clinic at baseline, followed by 5 additional visits via telephone at week 4, 6, 8, 12 and 24.
 
All participants will continue to receive standard care assessment, as undertaken by the NHS IAPT service, standard care high intensity psychological therapy intervention as clinically indicated and provided by the NHS IAPT service, and standard care pharmacological treatment as prescribed by the participant's GP. Participation in this study will not influence nor compromise standard care treatment – all study procedures are additional to standard care. Participation in the study will have no impact upon the duration of the waiting time for high intensity psychological therapy intervention.

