## STUDY FLOW CHART

Day 1 – Week 6 Initial Alpha-Stim AID CES treatment period with daily 60 minute sessions and pre and post anxiety scale completion.
	
Visit 1: Day 1 Baseline in clinic visit comprising informed consent, training in use of Alpha-Stim AID CES device, GAD-7, WASA, PHQ-9, EQ-5D-5L, Athens and CSRI.
	
Standard care Participant on waiting list (at least 6 - 8 weeks) for step three high intensity psychological therapy intervention, followed by assessment and at least two individual CBT sessions as required.

Week 6 – Week 12 Optional additional Alpha-Stim AID CES treatment period with daily 60 minute sessions and pre and post anxiety scale completion.
	
Visit 2: Week 4 Telephone visit comprising GAD-7, WASA, PHQ-9, EQ-5D-5L, Athens and treatment compliance and adverse events.
	

Visit 3: Week 6 Telephone visit comprising GAD-7, WASA, PHQ-9, EQ-5D-5L, Athens, CSRI and treatment compliance and adverse events. End of treatment for participants as requested.
	
Visit 4: Week 8 Telephone visit comprising GAD-7, WASA, PHQ-9, EQ-5D-5L, Athens and treatment compliance and adverse events.
	

Visit 5: Week 12 Telephone visit comprising GAD-7, WASA, PHQ-9, EQ-5D-5L, Athens and treatment compliance and adverse events. End of treatment for all participants.
	
Visit 6: Week 24 Telephone visit comprising GAD-7, WASA, PHQ-9, EQ-5D-5L, Athens and CSRI. End of study for all participants.
	

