#### 3.2 Secondary objectives

The secondary objective of this study is to evaluate the cost effectiveness of treatment with Alpha-Stim AID cranial electrotherapy stimulations (CES) for participants with a primary working diagnosis of generalised anxiety disorder (GAD), in terms of health and social care service cost, and patient cost, over the previous 12 weeks, from baseline to week 24, following previous treatment with low intensity psychological therapy intervention.

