**Visit 3: Week 6 (plus or minus 5 calendar days)**

The research nurse will telephone call the participant and undertake the following assessments:

- GAD-7
- EQ-5D-5L
- WASA
- PHQ-9
- Athens Insomnia Scale
- Check treatment compliance and anxiety log completion
- Check adverse events

The research nurse will administer these and record the data either directly into the electronic patient record (PCMIS) if available (and therefore the PCMIS record will act as source data), or into a Case Report Form (CRF) if not available (and therefore the CRF will act as source data) and then transpose the data into PCMIS or scan the CRF into the electronic file.

It is anticipated that these assessments will take approximately 30 minutes in total.

At this visit, the research nurse will discuss whether the participant wishes to continue with Alpha-Stim AID CES treatment in the same manner for an additional 6 weeks. If the participant does wish to do so, they will be advised that they must continue to complete the anxiety log book. The decision to continue or end treatment with Alpha-Stim AID CES will not impact upon access to stand care therapy interventions, and participants will be contacted by the IAPT service regardless of their decision at this time point. If the participant does not wish to continue with Alpha-Stim AID CES treatment, the research nurse will ask that they return the medical device via post.

The final treatment session should be completed immediately prior to the visit 3 assessments undertaken by the research nurse.

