### **11.3 Statistical analysis plan**

Mean and standard deviation scores will be reported for each visit time-point. The statistician who will deliver the analysis is:

[name]., PStat  
Professor – Psychometrics & Statistics  
Accredited Professional Statistician - American Statistical Association  
Director – Initiative for Interdisciplinary Research Design & Analysis (IIRDA)  
Texas State University  
[name]  
Email: [[contact]](mailto:[contact])

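### The flow chart contradicts sections 7.5 and 7.6 on when the CSRI is collected, no described tool records prescribed drugs, and the cost outcome is worded inconsistently

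*Combined protocol and SAP*

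**What the plan says.** **Outcome.** Section 3.2 sets the cost objective "over the previous 12 weeks, from baseline to week 24". Section 3.5 says the CSRI outcome "is the change in cost impact for previous 12 weeks from baseline to week 24". The study summary has no look-back and does not mention a change: "The endpoint will be the cost impact from baseline to week 24". The form in Appendix B asks about the last 3 months, not 12 weeks. Section 11.3 promises only this: "Mean and standard deviation scores will be reported for each visit time-point". It defines no cost total.

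**Schedule.** For week 6 the flow chart has: "Telephone visit comprising GAD-7, WASA, PHQ-9, EQ-5D-5L, Athens, CSRI and treatment compliance and adverse events". For week 12 it has: "Telephone visit comprising GAD-7, WASA, PHQ-9, EQ-5D-5L, Athens and treatment compliance and adverse events". The visit lists in section 7.5 and the table in section 7.6 show the reverse, with the CSRI at day 1, week 12 and week 24 and none at week 6.

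**Content.** Sections 3.5 and 7.4 present the CSRI as capturing the whole of health and social care cost plus patient cost. Appendix B covers outpatient, inpatient, primary and community care, travel, additional care and informal care. Its only medicine item concerns over-the-counter, herbal or complementary purchases. Section 4 keeps GP prescribing running as standard care, and section 1 names reduced pharmacological treatment as one way the device could save money.

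**The concern.** Cost effectiveness is the only secondary objective, and section 2 says the study is designed mainly to supply evidence to NICE and NHS England. A cost estimate for that purpose needs a defined period, forms that cover the period, and every major cost category.

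The schedule conflict threatens coverage. Service use that is not asked about at the right call is hard to recover later. The weeks at risk are those of the optional second device course, "which is likely to coincide with start of high intensity psychological therapy intervention as clinically indicated". Section 4 is more cautious and says only that the two may coincide.

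The missing prescription item threatens content: a drug saving that the protocol itself puts forward could be neither shown nor refuted. The loose outcome wording leaves the analyst to decide whether the week-12 form counts.

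**Working it through.** The plan states no figure for cost coverage, so the check compares passages and counts weeks.

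**1. Weeks of follow-up covered.** Each form looks back 12 weeks (sections 3.2 and 3.5) or 3 months (Appendix B), taken here as 91 days, or 13 weeks.

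| CSRI visits used | 12-week recall | 3-month recall |
|---|---|---|
| Day 1, week 12, week 24 (7.5, 7.6) | 12 + 12 = 24 of 24 | 24 of 24 |
| Day 1, week 6, week 24 (flow chart) | 6 + 12 = 18 of 24 (75%) | 6 + 13 = 19 of 24 (79%) |
| Day 1 and week 24 only (one reading of 3.5) | 12 of 24 (50%) | 13 of 24 (54%) |

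Under the flow chart the week-6 form reaches back past baseline and covers only weeks 0 to 6 of follow-up. The week-24 form starts at week 12, or at week 11 with 3-month recall. The gap is therefore weeks 6–12, or weeks 6–11.

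**2. Which visit the durations support.** Section 7.5 gives 30 minutes for each of weeks 4, 6 and 8, whose lists have no CSRI. Section 7.4 gives 15 minutes for the CSRI. 30 + 15 = 45, which is the time stated for week 12. Week 24 is also given 30 minutes although its list includes the CSRI; its tools sum to 5 × 5 + 15 = 40. That is a separate inconsistency and says nothing about week 6 against week 12.

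**3. Prescribed drugs.** Section 12.1 lists the GAD-7, EQ-5D-5L, CSRI, WASA, PHQ-9, Athens scale and anxiety log. Section 7.4 describes the log as anxiety ratings before and after each session. None is described as recording prescriptions, the 7.6 table has no medication row, and no extraction from GP records is described. Section 1 gives about £80 per 28 days as an example price for pregabalin.

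- On the drug throughout, 24-week total: 168 / 28 × £80 = £480 unrecorded.
- Starts or stops the drug, change between two 12-week periods: up to 84 / 28 × £80 = £240 unrecorded.
- On the drug throughout, change between two 12-week periods: £240 − £240 = £0.

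**4. Fixed 3-month recall with visit windows.** Calls may fall 5 days either side of the target (section 7.5).

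- Baseline to week-12 call: 84 ± 5 = 79 to 89 days. A 91-day look-back takes in 91 − 89 = 2 to 91 − 79 = 12 pre-baseline days.
- Week-12 to week-24 call: 84 ± 10 = 74 to 94 days. The result runs from 91 − 74 = 17 days counted twice to 94 − 91 = 3 days missed.

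**The case against.** The strongest reply concerns the outcome wording. The 12-week phrase may simply be the recall period of each form. With forms at weeks 12 and 24, two 12-week look-backs cover weeks 0 to 24 exactly, and the summary endpoint can be read as that total. This stands. A reader might infer from section 3.5 that the plan discards half of follow-up, but the documents do not establish that: under sections 7.5 and 7.6 the week 0–12 data are collected. What remains is an unclear definition, which can be settled before analysis.

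On the schedule, the flow chart is the outlier against the visit lists, the table and the durations. That makes the correction easy. It does not remove the risk that staff work from the chart.

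On drugs, section 12.1 is not a complete list of what is recorded, since adverse events and compliance are also captured, and the case report form itself is not among the documents. The claim is therefore limited to tools that are described. Section 1 also places antidepressants before pregabalin, so the £80 example need not be typical.

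Two further inferences are tempting and unsupported. One is to set £480 against the £465 device cost assumed in section 11.1, as if the omission cancelled the device cost. The £480 applies only to a cumulative total for a continuous user of one drug. The other is to treat the £2,895 therapy cost in section 11.1 as the size of the gap. That is a whole-course cost, weeks 12–24 are covered on every reading, and the share falling in weeks 6–12 is not given.

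**Conclusion.** The point holds in three parts of unequal strength.

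- **Schedule conflict:** explicit in the text. Following the flow chart would leave 5 to 6 of 24 follow-up weeks uncosted; following sections 7.5 and 7.6 leaves none.
- **Prescribed drugs:** a substantive gap. With the tools as described, a change in prescription cost cannot be shown. The £480 and £240 figures are per user at the protocol's example price. No mean error can be given, because the share of users and the prices of other drugs are not stated, and the direction of any error is unknown.
- **Cost outcome:** a matter of clarification. On one reading the week-12 form enters no defined outcome and only weeks 12–24 count after baseline; on another it is half of a 24-week total. The text does not settle which.

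The week counts assume 3 months is 91 days and, in the coverage table, calls on their exact dates. None of this touches the primary GAD-7 outcome. It should be put right before CSRI data are collected, because the missing items would be hard to reconstruct.

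**What to change.** 1. Correct the flow chart to match sections 7.5 and 7.6: CSRI at day 1, week 12 and week 24, and not at week 6.
2. Add a prescribed-medicine item to the CSRI (name, strength, quantity, duration), asked at all three CSRI visits.
3. Reconcile section 3.2, section 3.5 and the study summary. State that the 24-week cost is the week-12 CSRI plus the week-24 CSRI plus device and consumable cost at a stated price. Section 11.1 assumes £465, while section 8.2 gives £499 as the private purchase price. Report the change from the pre-baseline 12 weeks as well, since it is the only within-study cost contrast in a single-arm design.
4. Anchor recall at week 12 to the time since baseline, and at week 24 to the time since the week-12 call, in place of a fixed 3 months.

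The cost is some protocol wording, one flow chart entry, a short form revision, a few more minutes per CSRI call, and an amendment notified under section 14.9. The week-12 CSRI is already scheduled, so no visit is added.
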